5.2 Method of Assignment to Treatment

Not applicable. All patients in the extension study will receive deferiprone.

5.3 Blinding Procedures

This study is open-label, with all participants receiving deferiprone. However, patients, study staff, and members of the ApoPharma study team will remain blinded during the extension study with regard to whether the patients had received deferiprone or placebo in the initial study. The blind will be broken once the initial study is completed.

5.4 Allocation of Patient Numbers

All patients who signed the ICF for study TIRCON2012V1 will have been assigned a unique 6-digit number, where the first 3 digits represent the site code and the last 3 are sequentially assigned to each patient. These assigned numbers will be maintained for patients who continue on to study TIRCON2012V1-EXT.

5.5 Treatment Compliance

At each visit, patients will be instructed to bring empty and unused containers of study medication back to the study site. Compliance will be evaluated by calculating the volume of medication dispensed and the volume of unused drug supply remaining in the bottle.

6 STUDY TREATMENTS

All patients in the extension study will receive deferiprone.

6.1 Investigational Product

Deferiprone (3-hydroxy-1,2-dimethylpyridin-4-one) is manufactured by Apotex Inc. The drug will be supplied to the clinical sites by ApoPharma Inc.

6.1.1 Dosage Form and Mode of Administration

Deferiprone will be provided as an 80 mg/mL oral solution. It is to be taken orally, twice a day, and can be taken with or without food, as per the investigator's recommendation.

6.1.2 Precautions for Use

Bottles should not be stored in direct light. The contents of a bottle must be used within 8 weeks of opening.

6.2 Reference Product

Not applicable. All participants in study TIRCON2012V1-EXT will receive deferiprone.

6.3 Packaging and Labeling

Deferiprone 80 mg/mL oral solution will be supplied in 500 mL amber-colored bottles with child-resistant closure and a tamper-evident seal. The containers will be provided with labels whose content is in accordance with all applicable regulatory requirements. The label will include protocol number, expiry date, lot/batch number, investigational statement, storage temperature, dosage, direction for use, visit number, date dispensed, and name and address of the study sponsor.

6.4 Shipping and Storage

A "Product Receipt Form and Temperature Verification Log" will be provided to the study sites by the sponsor with each shipment of investigational product. The investigator or a designate is to sign and date this receipt form to acknowledge receiving the entire product shipment in good condition, and to record the time at which the "TempTale 4" (Sensitech Inc.) temperature-monitoring device was removed and stopped. The site will fax a copy of this receipt form to the sponsor and retain the original in its Investigator Trial File.

The study medication is to be stored in a secure location (a locked room or cabinet), under the control of the investigator and with access to authorized individuals only, at room temperature (15–30 °C [59–86 °F]). The sites will use a digital temperature monitoring device and a temperature log to facilitate daily recording of the temperature of the storage facility.

6.5 Product Accountability

It is the responsibility of the investigator to ensure that all study drug received at the study center is inventoried and accounted for throughout the study. Records of receipt, storage and administration of the study drug supplied must be maintained, and the drug accountability will be verified by the sponsor or sponsor's designee during on-site monitoring visits. At the conclusion of the study, a final inventory must be performed by the investigator or delegate. The sponsor will be responsible for determining the specific conditions for destruction of unused product.

The investigator must maintain logs of the quantity of product received from the sponsor and of the quantity dispensed to each patient, as follows:

Site Investigational Drug Inventory Record:

- Name of sponsor
- Name of investigator
- Study identifier
- Date and quantity of investigational product received from the sponsor
- Lot/batch number
- Study medication bottle number

Patient Investigational Drug Dispensing Record:

- Patient identification number
- Date of dispensing and return
- Dispenser's initials
- Quantity dispensed and returned
- Study medication bottle number

6.6 Replacement Doses

Patients will be dispensed a 6-month supply of study medication at Visit 1 (Week 0), Visit 2 (Week 26), and Visit 3 (Week 52). Dispensing must be done by appropriately qualified staff (physician, pharmacist, or nurse).

If a patient reports that medication has been lost or accidentally destroyed, the appropriate site staff member must make a request for replacement medication, in writing, to the Clinical Research Associate (CRA), who will review and forward the request to the sponsor. All information related to the replacement medication is to be recorded in the drug accountability forms.

6.7 Disposition of Unused Product

It is the responsibility of the investigator to ensure that all study drug received at the study center is inventoried and accounted for throughout the study. Records of receipt, storage and administration of the study drug supplied must be maintained, and the drug accountability will be verified by the sponsor or sponsor's designee during on-site monitoring visits. At the conclusion of the study, a final inventory must be performed by the investigator or delegate. The sponsor will be responsible for determining the specific conditions for destruction of unused product.

7 MEASUREMENTS AND EVALUATIONS

7.1 Efficacy Measurements

7.1.1 Barry-Albright Dystonia Scale

Dystonia is a neurological movement disorder in which sustained muscle contractions cause twisting and repetitive movements or abnormal postures. The Barry-Albright Dystonia (BAD) scale is a reliable and responsive measure for rating the degree to which dystonia interferes with function (27). A 5-point ordinal scale is used to rate the severity of dystonia in 8 body regions: eyes, mouth, neck, trunk, and each upper and each lower extremity. The individual scores are then summed to provide a total score that ranges from 0 to 32; the higher the score, the more severe the dystonia. See [Appendix 4](#).

For study TIRCON2012V1, a protocol was prepared by a group of experts to define a standardized way to administer and read the BAD scale, including a provocation test to better capture episodic or non-continuous symptoms. The administration of the BAD scale by the investigator or delegate is videotaped, and the videotape is sent to a central evaluator for objective assessment. The results will be sent back to the site, and will be entered by the study site staff into the eCRF.

In study TIRCON2012V1-EXT, the BAD scale will be administered at Visits 1, 2, 3, and 4 (or early termination visit).

7.1.2 Patient Global Impression of Improvement

The Patient Global Impression of Improvement (PGI-I) is a global index used to rate the response of a condition to a therapy. Patients are asked at each post-Week 0 visit to rate their overall condition since Visit 1 of the extension study on a 7-point rating scale: 1 = very much improved, 2 = much improved, 3 = minimally improved, 4 = no change, 5 = minimally worse, 6 = much worse, and 7 = very much worse. In cases where the patient cannot complete the scale by him/herself, the parent or legal representative will complete the scale. See [Appendix 5](#).

The PGI-I will be administered at Visits 2, 3, and 4 (or early termination).

7.2 Safety Measurements

7.2.1 Adverse Events and Serious Adverse Events

7.2.1.1 Definition of Adverse Events

An adverse event (AE) is any untoward medical occurrence in a patient who is administered a pharmaceutical or other therapeutic product in a clinical study, not necessarily having a causal relationship with the product. An AE can therefore be any unfavorable and unintended sign, symptom, or disease temporally associated with the use of a product, whether or not considered related to that product.

AEs include:

- Exacerbation of a pre-existing illness, including acute episodes/crisis of a chronic underlying condition
- An increase in frequency or intensity of a pre-existing episodic event or condition
- A condition detected or diagnosed after study treatment administration, even though it may have been present prior to the start of the study
- A continuous persistent disease or symptom present at baseline that worsens following the start of the study
- Accidents (e.g., involving a motor vehicle)
- Reasons for changes in concomitant medication (type of drug and/or dose)
- Medical, nursing, or pharmacy consultation
- Admission to hospital and surgical operations
- Abnormalities in laboratory findings (e.g., blood chemistry, hematology, urinalysis), ECG, or other assessments (e.g., vital signs) that are not part of a larger medical condition already recorded as an AE and which are judged by the investigator to be clinically significant. The investigator should exercise medical and scientific judgment in deciding whether an abnormal laboratory finding or other abnormal assessment is clinically significant.

AEs do not include:

- A pre-existing disease or condition present or detected at the start of the study that does not worsen
- Hospital admissions or surgical procedures that had been planned prior to enrolment into the study

- The disease or disorder being studied, or a sign or symptom associated with that disease or disorder, unless it has worsened
- An overdose of either the study treatment or concurrent medication without any signs or symptoms

Note: A case of overdose that is not associated with an AE is to be documented as a protocol deviation and promptly reported to the Medical Monitor.

7.2.1.2 Monitoring and Documenting of Adverse Events

AEs will be collected until 14 days after the last dose, and SAEs will be collected until 30 days after the last dose.

AEs and SAEs that are related to the underlying medical condition for which the patient enrolled in the clinical trial will be recorded separately from others.

Patients will be instructed to report any AEs to the investigator or a delegate. In addition, the investigator will solicit information about the occurrence of AEs through open-ended, non-leading verbal questions such as:

- How are you feeling?
- Have you had any medical problems since the last visit?
- Have you taken any new medications, other than those provided in this study, since the last visit?

Based on the patient's response to these questions, the investigator or delegate should ask additional questions relevant to the specific complaint, such as:

- How severe is/was the symptom?
- How often did the symptom occur?
- How long did the symptom last?

The patient should also be questioned about any previously reported AEs that have not resolved.

The investigator will evaluate all AEs for their relationship to the investigational product ([Section 7.2.1.3](#)), intensity ([Section 7.2.1.4](#)), and seriousness ([Section 7.2.1.5](#)), and will document any measures taken to address the event. There should be an attempt to establish a diagnosis of the AE based on signs, symptoms, and/or other clinical information. Wherever possible, a diagnosis should be documented, rather than the individual signs/symptoms. All information is to be clearly recorded in the source documents.

If the dosage of study drug is reduced or treatment is discontinued as a result of an AE, the circumstances leading to such reduction or discontinuation must be clearly documented.

All AEs must be followed until resolution, the condition stabilizes, the event is otherwise explained, or the patient is lost to follow-up. The investigator is responsible for ensuring that follow-up includes any supplemental investigations that are needed to elucidate the nature and/or causality of the AE as completely as possible. This may include additional laboratory tests or investigations, histopathological examinations, or consultation with other health care professionals.

7.2.1.3 Assessment of Causality

The relationship of an AE to the study drug should be determined by the investigator after thorough consideration of all available facts, including associative connections (time or place), pharmacological explanations, previous knowledge of the drug, presence of characteristic clinical or pathological phenomena, exclusion of other causes, and/or absence of alternative explanations. The causal relationship of an adverse event to study drug will be assessed according to the following criteria (based on World Health Organization definitions):

- Not related: Temporal relationship to study drug administration is missing or implausible, or there is no evident cause.
- Possibly related: Reasonable time sequence to administration of study drug, but event could also be explained by concurrent disease or other drugs or chemicals.
- Probably related: Reasonable time sequence to administration of study drug, and unlikely to be attributed to concurrent disease or other drugs or chemicals, and follows a clinically reasonable response on withdrawal (de-challenge). Re-challenge information is not required.
- Definitely related: Plausible time relationship to study drug administration, and cannot be explained by concurrent disease or other drugs or chemicals. The response to withdrawal of the drug (de-challenge) should be clinically plausible. The event must be definitive pharmacologically or phenomenologically, using a satisfactory re-challenge procedure if necessary.

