4.5 Patient Withdrawal

Patients have the right to withdraw from the study at any time and for any reason without consequence to future care by the investigator or study center.

A patient may be withdrawn from the study at any time, at the discretion of the investigator, for any of the following reasons:

- Medical or safety reasons considered significant by the patient and/or the investigator
- Requirement for concomitant medication that might interfere with the evaluation of study treatment or may be contraindicated
- Occurrence of other illnesses that might affect the patient's further participation in the study or evaluation of study treatment
- A protocol deviation that might interfere with study assessments, as judged by the investigator
- Repetitive patient non-compliance with the protocol or with instructions of the investigator
- Participation in another clinical trial at any time during the conduct of this study
- Any other situation where, in the opinion of the investigator, continuation of the study would not be in the best interest of the patient

A patient **must** be withdrawn from the study if any of the following conditions apply:

- Pregnant or planning to become pregnant (see [Section 7.2.4](#), Procedures in Case of Pregnancy)

- Occurrence of any adverse event characterized as life-threatening or disabling that is not associated with the patient's primary diagnosis and that is assessed as at least possibly related to study drug by the investigator or the sponsor
- Non-compliance with weekly hematology blood counts (3 or more consecutively missed visits will result in automatic withdrawal)
- Termination of the study by the sponsor
- Occurrence of moderate neutropenia or severe neutropenia/agranulocytosis (see [Section 7.2.1.8](#), Adverse Events of Special Interest)

Patients who decide to withdraw participation in the study should always be contacted, if possible, in order to ask about the reason for withdrawal, whether any adverse events (AEs) occurred, and use of concomitant medications. A withdrawn patient should return for an Early Termination Visit. All investigational product and materials should be returned. If any AEs occurred, the investigator must attempt to follow up the outcome for 30 days post-termination.

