8 STUDY COMMITTEES

Data Safety Monitoring Board

An independent Data Safety Monitoring Board (DSMB) was established prior to the start of study TIRCON2012V1 to monitor patient safety, and will be maintained during the extension study. The DSMB is responsible for overseeing the conduct of the trial, and is empowered to

recommend stopping the trial if, in its members' judgment, continuation is not ethically acceptable on the grounds of safety.

The following will trigger an evaluation by the DSMB for recommending stopping the study at any time point:

1. Death or life-threatening event that is deemed to be at least possibly related to the study medication by either the investigator or the sponsor
2. Occurrence of serious adverse events that:
 - Are not associated with exacerbation of a pre-existing condition, and
 - Are deemed to be at least possibly related to the study medication by either the investigator or the sponsor, and
 - Affect at least 2 patients

No study-stopping decision will be made without prior consultation with the sponsor, the FDA, and the EMA.

The operating model and the frequency of the interim safety review meetings are laid out in the DSMB charter.

The DSMB will be notified of any changes to the protocol or the study conduct, and will be included in the review of any substantive changes to the protocol that could affect patient safety prior to the submission of these changes to the IRB/IEC for implementation approval.

All DSMB meeting minutes and board composition will be submitted to the regulatory authorities with the final clinical study report.

Extension Study Scientific Steering Committee

This committee was established to provide scientific guidance and to maintain control over the study data and its dissemination. Details of the committee are provided in [Appendix 6](#).

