4.4.1 Adverse Events

A summary table of adverse events will include the following information:

- number of patients exposed to study treatment,
- number of patients experiencing at least one AE,
- number of patients experiencing at least one severe AE,

- number of patients experiencing at least one serious AE,
- number of patients experiencing at least one drug-related AE,
- number of deaths,
- total number of patients withdrawn,
- number of withdrawals due to AEs.

All adverse experiences will be coded using MedDRA (Medical Dictionary for Regulatory Activities) and will be summarized by MedDRA System Organ Class (SOC) and Preferred Term. Adverse events will be defined as: 1) AEs that occurred or worsened (increased in intensity and/or frequency) on or after the first dose of study medication, 2) AEs with a missing start date or a stop date on or after the first dose of study medication, 3) AEs with both a missing start and stop date. Events that occur within 14 days after treatment discontinuation will also be considered AEs. Serious adverse events that occur within 30 days after treatment discontinuation will be included in the database.

Adverse events will be summarized using the total number of AEs, the total number and percent of patients who experience an AE, and the number and percent of patients who experienced an AE within each SOC (and preferred term within an SOC). The rate of each AE (per 100 patient years) will also be calculated. AEs will also be presented by intensity (mild, moderate, severe), by seriousness (serious, non-serious), and by relationship to study medication (at least possibly related, not related). The number and percentage of patients who are withdrawn from the study due to AEs will be calculated, and the AEs involved will be summarized in a frequency table. Time to onset and duration of all AEs with an incidence of >5%, and of any AEs of special interest (e.g., worsening of dystonia), will be summarized with descriptive statistics.

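### The 'not related' definition is ambiguous, and read literally it is the only category that fits a well-timed, unexplained adverse event with no de-challenge information

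*Protocol*

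**What the plan says.** Protocol 7.2.1.3 sets four causality categories, and says causality will be assessed according to them.

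- *Not related* is met by either of two conditions: "Temporal relationship to study drug administration is missing or implausible, or there is no evident cause".
- For *possibly related* the wording is "Reasonable time sequence to administration of study drug, but event could also be explained by concurrent disease or other drugs or chemicals", so a rival explanation is part of that category.
- For *probably related* the timing must be reasonable and the event must be "unlikely to be attributed to concurrent disease or other drugs or chemicals, and follows a clinically reasonable response on withdrawal (de-challenge"). The text waives re-challenge information for this category but gives no such waiver for de-challenge.
- For *definitely related* the Protocol asks for plausible timing, no other explanation and a plausible response to withdrawal, and in addition states: "The event must be definitive pharmacologically or phenomenologically, using a satisfactory re-challenge procedure if necessary".

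The paragraph introducing the categories lists the exclusion of other causes and the absence of alternative explanations among the facts to weigh.

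SAP 4.4.1 presents adverse events "by relationship to study medication (at least possibly related, not related"), and Protocol 9.4.1.4 uses the same two-way split. Relatedness is a listed attribute of the AE and SAE endpoints in Protocol 9.1.1. The same threshold is used in Protocol 4.5, where mandatory withdrawal applies to certain events "assessed as at least possibly related to study drug by the investigator or the sponsor", and in Protocol 8, where DSMB evaluation is triggered by events "deemed to be at least possibly related to the study medication by either the investigator or the sponsor".

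**The concern.** In the introductory paragraph and in the two strongest categories, failing to find another cause makes the drug more likely. In *not related*, failing to find a cause is enough on its own to clear the drug, whatever the timing. Investigators at several sites could therefore put the same event on opposite sides of the reported boundary.

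The judgement carries weight here because the study is single-arm, with every patient on deferiprone. No concurrent control group shows how often an event would have occurred anyway, so the related/unrelated split rests on the causality assessment. The SAP outputs that depend on it are the ADR count in Table 14.3.1.1, the related/unrelated Table 14.3.1.7, and Table 14.3.1.8 on ADRs above 5%, whose shell also carries time to onset and duration.

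**Working it through.** The plan gives no figure to reproduce. The check applies the four definitions, as worded, to each combination of timing, competing explanation and de-challenge.

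| Case | Timing | Other explanation | De-challenge | Categories whose wording fits | Reported side |
|---|---|---|---|---|---|
| A | Reasonable | None | Supportive | *Probably*; arguably also *not related* | Both |
| B | Reasonable | None | Absent or unknown | *Not related* only | Not related |
| C | Reasonable | Available | Any | *Possibly* | Related |
| D | Missing or implausible | Any | Any | *Not related* | Not related |

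**Case A.** The event meets *probably related*. It also meets *not related* if *cause* is taken to mean a cause other than the drug. This overlap depends on the reading.

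**Case B.** *Possibly related* fails because no concurrent disease or other drug could explain the event. *Probably* and *definitely related* fail because there is no withdrawal response to assess. An unexplained death on treatment is one example. So is any non-serious event that runs its course without study drug being stopped.

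**Cases B and C together.** With timing equal, an event that has a rival explanation is reported as related, while one with no rival explanation is reported as not related. That ordering contradicts the introductory paragraph.

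**Case D.** No conflict.

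**The other reading.** Suppose the phrase means that no causal link to the drug is evident. Case A is then resolved in favour of *probably related*. Case B is not resolved: either the investigator sees no link and chooses *not related*, or the timing counts as a link and the event fits no category. The gap in case B survives both readings.

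**Leverage of one event.** SAP 3.2 gives 68 enrolled patients (44 + 24). If all took a dose, one patient is 1/68 = 1.5%. The Table 14.3.1.8 cut-off of more than 5% corresponds to 0.05 × 68 = 3.4, so at least 4 patients (4/68 = 5.9%; 3/68 = 4.4%). Taking an ADR to be an event judged at least possibly related, one patient crossing the boundary can remove a preferred term that stands at 4.

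One rule dampens this. SAP 4.4.1 counts a patient once per term, by the event with the closest relationship to the drug. The patient count therefore moves only if that patient has no other related event under the same term. Event counts move with every event.

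**The case against.** The best defence is that these bullets grade the relationship to study drug, so the phrase most naturally means that no link to the drug is evident. An event with good timing, no rival explanation and recovery on withdrawal does have an evident cause, namely the drug. The introductory paragraph already asks the investigator to weigh the absence of alternatives, and Protocol 7.2.1.2 requires follow-up to clarify causality. This defence has force against the overlap in case A. It does not settle case B, and nothing elsewhere in the Protocol or SAP says which meaning is intended.

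A reader might infer that any well-timed event without another explanation meets both *probably related* and *not related*, so that the scale is simply reversed. The documents do not support that. *Probably related* also requires a response to withdrawal, so only events with supportive de-challenge can overlap, and then only on one reading.

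A reader might also infer that every relatedness-based safeguard is undermined. That too goes further than the text:

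- The withdrawal rule and the DSMB triggers accept the sponsor's assessment as well as the investigator's.
- All SAEs up to 30 days after completion or discontinuation go to the sponsor whatever their suspected cause (Protocol 7.2.1.6).
- Moderate and severe neutropenia require withdrawal without a causality judgement (Protocol 4.5), and every grade requires an SAE form (Protocol 7.2.1.8).
- Incidence by SOC and preferred term, by severity and by seriousness does not use relatedness.

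The protection is partial. It does not reach non-serious events, and no sponsor assessment is specified for the relatedness tables.

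**Conclusion.** The concern holds in a limited form. The second condition of *not related* is ambiguous. Read literally, it leaves a well-timed, unexplained event without de-challenge information no category except *not related*. With supportive de-challenge, the same event meets *probably related* and arguably *not related* too.

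The effect is misclassification toward unrelated in the two-way relatedness summaries, mainly for non-serious events. The number of such events cannot be derived from the documents. Each one crosses the reported boundary, because the tables have no intermediate class.

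This conclusion assumes that investigators apply the definitions as worded. For patients who received deferiprone in the initial study, the safety period starts in that study. Its protocol is not among these documents, so whether the same wording governed those earlier assessments is unknown.

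**What to change.** In Protocol 7.2.1.3:

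1. Replace the second condition of *not related*, so that the category requires either missing or implausible timing, or an event clearly accounted for by a cause other than study drug. The word *clearly* matters. A looser condition, such as the mere presence of another evident cause, would overlap with *possibly related*, which covers events that another cause could also explain.
2. Add that the absence of an alternative cause does not by itself make an event unrelated.
3. Add that well-timed events with no other explanation and no de-challenge information are classed as at least possibly related.

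The cost is one phrase and two sentences. The two-way split, the table shells, and the withdrawal and DSMB rules can stay as they are. If events have already been assessed under the present wording, those marked *not related* with reasonable timing and no recorded alternative cause should be re-checked before database lock. Otherwise the tables would mix two definitions.
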